8.2.1 Clinical Evaluations

Radiographic or other imaging assessments.

N/A

8.2.2 Biospecimen Evaluations

Biological specimen collection and laboratory evaluations. In addition to the clinical blood samples, subject will have research bloods drawn within the blood withdrawal volume limits established by the Clinical Center. RNAseq, Flow cytometry, metabolomics, HDL cholesterol uptake and cytokine profiling may be performed. Skin biopsy samples may be obtained for culture or isolation of distinct cell populations for subsequent biochemical, cell biological and molecular analyses and for immune-histochemistry. With the patient's consent, a biopsy each of lesional skin (where there is active psoriasis) and non-lesional sites (where there is no psoriasis) will be performed, and hemostasis will be achieved. The skin biopsy will be performed by a healthcare provider and will be used primarily for research purposes.

Abbreviated Title: NR in psoriasis

Version Date: 07/21/2023

Test/assay	Volume blood (approx.)	Type of tube	Collection point (+/- 48hrs)	Location of specimen analysis
Immune-monitoring	80 mls for PBMC's and NAD+. 20mls for Neutrophils. 20mls for low density granulocytes (LDG's).	Green Tops for PBMC's and NAD+ Green Tops for Neutrophils Green Tops for LDG's	Baseline and 4 weeks.	[name] Lab (Deliver to [name] lab)
HDL reverse transport	5-10mls (for serum)	Red top	Baseline and 4 weeks	[name] lab

8.2.3 Correlative Studies for Research/Pharmacokinetic Studies

N/A

8.2.4 Samples for Genetic/Genomic Analysis

N/A

8.3 SAFETY AND OTHER ASSESSMENTS

Laboratory tests will be assessed at baseline and at 4 weeks. Adverse event review will occur at 4 weeks.

Counseling: Subjects should maintain a stable diet and not start any new diets or exercise programs for the duration of the study.

8.4 ADVERSE EVENTS AND SERIOUS ADVERSE EVENTS

8.4.1 Definition of Adverse Event

Adverse event means any untoward medical occurrence associated with the use of an intervention in humans, whether or not considered intervention-related (21 CFR 312.32 (a)).

8.4.2 Definition of Serious Adverse Events (SAE)

Abbreviated Title: NR in psoriasis

Version Date: 07/21/2023

An adverse event (AE) or suspected adverse reaction is considered "serious" if, in the view of either the investigator, it results in any of the following outcomes: death, a life-threatening adverse event, inpatient hospitalization or prolongation of existing hospitalization, a persistent or significant incapacity or substantial disruption of the ability to conduct normal life functions, or a congenital anomaly/birth defect. Important medical events that may not result in death, be life-threatening, or require hospitalization may be considered serious when, based upon appropriate medical judgment, they may jeopardize the participant and may require medical or surgical intervention to prevent one of the outcomes listed in this definition. Examples of such medical events include allergic bronchospasm requiring intensive treatment in an emergency room or at home, blood dyscrasias or convulsions that do not result in inpatient hospitalization, or the development of drug dependency or drug abuse.

8.4.3 Classification of an Adverse Event

8.4.3.1 Severity of Event

This study will utilize the Common Terminology Criteria for Adverse Events version 5.0 (CTCAE v5.0) for toxicity and adverse event reporting. A copy of the CTCAE v5.0 can be downloaded from the https://ctep.cancer.gov/protocolDevelopment/electronic_applications/ctc.htm.

AEs classified as Grade 2-5 will be recorded, verified, and followed until satisfactory resolution or stabilization. In the event of any treatment-related SAEs, enrollment will be suspended until discussed with the IRB and Clinical Director.

Grading and attribution of adverse events

Severity definitions found in the CTCAE v5.0 will be used for grading the severity (intensity) of AEs:

- 1) **Mild:** Asymptomatic or mild symptoms; clinical or diagnostic observations only; intervention not indicated.
- 2) **Moderate:** Minimal, local or noninvasive intervention indicated; limiting age-appropriate instrumental ADL*
- 3) **Severe:** Severe or medically significant but not immediately life-threatening; hospitalization or prolongation of hospitalization indicated; disabling; limiting self-care ADL**.
- 4) **Life- threatening:** Life-threatening consequences; urgent intervention indicated.
- 5) **Death:** Death related to AE.

*Instrumental ADL refer to preparing meals, shopping for groceries or clothes, using the telephone, managing money, etc.

**Self-care ADL refer to bathing, dressing and undressing, feeding self, using the toilet, taking medications, and not bedridden.

8.4.3.2 Relationship to Study Intervention

- All Grade 2-5 adverse events (AEs) must have their relationship to study intervention assessed by the investigator or designee who examines and evaluates the participant based on temporal relationship and his/her clinical judgment. The degree of certainty

Abbreviated Title: NR in psoriasis

Version Date: 07/21/2023

about causality will be graded using the categories below. In a clinical trial, the study product must always be suspect.

- **Definitely Related** – There is clear evidence to suggest a causal relationship, and other possible contributing factors can be ruled out. The clinical event, including an abnormal laboratory test result, occurs in a plausible time relationship to study intervention administration and cannot be explained by concurrent disease or other drugs or chemicals. The response to withdrawal of the study intervention (dechallenge) should be clinically plausible. The event must be pharmacologically or phenomenologically definitive, with use of a satisfactory rechallenge procedure if necessary.
- **Probably Related** – There is evidence to suggest a causal relationship, and the influence of other factors is unlikely. The clinical event, including an abnormal laboratory test result, occurs within a reasonable time after administration of the study intervention, is unlikely to be attributed to concurrent disease or other drugs or chemicals, and follows a clinically reasonable response on withdrawal (dechallenge). Rechallenge information is not required to fulfill this definition.
- **Potentially Related** – There is some evidence to suggest a causal relationship (e.g., the event occurred within a reasonable time after administration of the trial medication). However, other factors may have contributed to the event (e.g., the participant's clinical condition, other concomitant events). Although an AE may rate only as "possibly related" soon after discovery, it can be flagged as requiring more information and later be upgraded to "probably related" or "definitely related", as appropriate.
- **Unlikely to be related** – A clinical event, including an abnormal laboratory test result, whose temporal relationship to study intervention administration makes a causal relationship improbable (e.g., the event did not occur within a reasonable time after administration of the study intervention) and in which other drugs or chemicals or underlying disease provides plausible explanations (e.g., the participant's clinical condition, other concomitant treatments).
- **Not Related** – The AE is completely independent of study intervention administration, and/or evidence exists that the event is definitely related to another etiology. There must be an alternative, definitive etiology documented by the clinician.]

8.4.3.3 Expectedness

The PI or designee will be responsible for determining whether an adverse event (AE) is expected or unexpected. An AE will be considered unexpected if the nature, severity, or

frequency of the event is not consistent with the risk information previously described for the study intervention. We expect some vasovagal symptoms during blood draws (expected frequency 50%) and transient bruising at the site of blood draws (expected frequency 50%).

8.4.4 Time Period and Frequency for Event Assessment and Follow-Up

The occurrence of an adverse event (AE) or serious adverse event (SAE) may come to the attention of study personnel during study visits and interviews of a study participant presenting for medical care, or upon review by a study monitor.

Abbreviated Title: NR in psoriasis

Version Date: 07/21/2023

Investigators will assess the occurrence of AEs and SAEs at all patient evaluation time points during the study. Grade 2 – 5 AEs/SAEs whether volunteered by the patient, discovered by study personnel during questioning, or detected through physical examination, clinically significant laboratory test, or other means will be recorded on the appropriate case report form. .

Information to be collected on Grade 2-5 AE/SAE includes event description, time of onset, clinician's assessment of severity, relationship to study product (assessed only by those with the training and authority to make a diagnosis), and time of resolution/stabilization of the event. All Grade 2-5 AEs will be followed to adequate resolution or stabilization.

Abnormal laboratory values not associated with clinical symptoms (except for grade 2 elevated liver enzymes) will be evaluated but will not be considered an AE. The laboratory results will be monitored by healthcare professionals and documented if clinically significant by the MD or any AIs in the study.

Psoriasis is a chronic disease associated with flares and we will record this information in the medical record.

Any medical condition that is present at the time that the participant is screened will be considered as baseline and not reported as an AE. However, if the study participant's condition deteriorates at any time during the study, it will be recorded as an AE.

Changes in the severity of an AE will be documented to allow an assessment of the duration of the event at each level of severity to be performed. AEs characterized as intermittent require documentation of onset and duration of each episode.

The PI or designee will record all reportable events with start dates occurring any time after informed consent is obtained until 7 days (for non-serious AEs or SAEs) after the last day of study participation. At each study visit, the team member will inquire about the occurrence of AE/SAEs since the last visit. Events will be followed for outcome information until resolution or stabilization.

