7 STUDY INTERVENTION DISCONTINUATION AND PARTICIPANT DISCONTINUATION/WITHDRAWAL

7.1 Discontinuation Of Study Intervention

The supplement has a good safety record and we do not expect any significant adverse events. However, if a grade 3 or higher adverse event related to the supplement occurs, the study will be halted pending discussions with the NIH IRB and the NHLBI Clinical Director.

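### Section 8.4.4 sets no grade above which a symptom-free laboratory abnormality becomes an AE, so on a literal reading a related grade 3–4 value escapes the automatic halt, required attribution and required follow-up (low severity)

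*Combined protocol and SAP*

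**What the plan says.** The rule on abnormal results is in section 8.4.4: "laboratory values not associated with clinical symptoms (except for grade 2 elevated liver enzymes) will be evaluated but will not be considered an AE". A further sentence has healthcare professionals monitor the results, with documentation where a study physician or associate investigator finds them clinically significant. No grade is named above which a symptom-free value counts as an AE. The only exception names a single grade of liver enzyme elevation.

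Several safety provisions start from the AE:

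- Section 7.1: "if a grade 3 or higher adverse event related to the supplement occurs, the study will be halted", pending discussion with the IRB and the Clinical Director.
- Section 8.4.4: "All Grade 2-5 AEs will be followed to adequate resolution or stabilization". Section 8.4.3.1 has a matching duty.
- Section 8.4.3.2 requires a judgement of relationship for every grade 2–5 AE.
- Footnote B of the Schedule of Activities offers an unscheduled safety visit for clinically significant AEs that are still ongoing. All its procedures are optional.

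Other text leans the opposite way. The AE definition in 8.4.1 does not require symptoms. Section 8.4.4 itself says that grade 2–5 events "detected through physical examination, clinically significant laboratory test, or other means will be recorded on the appropriate case report form". The causality categories in 8.4.3.2 mention abnormal laboratory results. Section 8.4.2 gives "blood dyscrasias or convulsions that do not result in inpatient hospitalization" among its examples of serious events, and 8.4.3.1 adds: "In the event of any treatment-related SAEs, enrollment will be suspended until discussed with the IRB and Clinical Director".

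**The concern.** A stopping rule works only if the findings it is meant to catch fall within its defined term. Severe laboratory abnormalities can be silent, and the protocol treats laboratory values as relevant to safety: section 5.2 excludes subjects on creatinine and ALT limits, and panels are drawn at baseline and Day 28. Yet 8.4.4 removes symptom-free values from the AE category whatever their grade. Two investigators could meet the same value, one applying the laboratory sentence and the other the clauses that lean the opposite way, and each could claim to follow the protocol.

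Two things are at stake. For subjects still dosing or about to start, it is whether a related severe abnormality in someone else stops the study without anyone having to exercise discretion. For the affected subject, it is whether the value is attributed and followed until it resolves.

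**Working it through.** The plan gives no figure to reproduce, and no arithmetic applies. The check takes one case, a symptom-free, supplement-related, non-hepatic grade 3–4 value, and asks of each provision what it acts on and whether the case reaches it under the 8.4.4 laboratory sentence.

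| Provision | Acts on | Reached? |
|---|---|---|
| 7.1 halt (mandatory) | Related AE, grade 3 or higher | No |
| 8.4.3.2 attribution | Grade 2–5 AE | No |
| 8.4.3.1 and 8.4.4 follow-up | Grade 2–5 AE | No |
| Footnote B visit | Ongoing clinically significant AE | No |
| 8.4.3.1 enrolment suspension | Treatment-related SAE | Unclear |
| 8.4.4 evaluation, and documentation if clinically significant | Abnormal laboratory value | Yes |
| 7.2 safety visit | Any treated subject before removal | Yes, but for completers it is Visit 2 |
| 8.5 unanticipated problem | Any occurrence meeting three criteria | Yes, if all three are met |
| Study Discontinuation and Closure (the second section numbered 10.1) | Sufficient cause, including unacceptable risk | At discretion |
| 10.4 DSMB | Safety data, at least semiannually | Possibly; data elements are set at its first meeting |

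**Do the other clauses restore AE status?** Not expressly.

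- The wording on detection by laboratory test describes how an AE may come to light. It can be confined to abnormalities that have symptoms or fall under the liver enzyme exception.
- The same holds for the causality wording in 8.4.3.2.
- The general definition in 8.4.1 would include the value, but the laboratory sentence is the more specific rule.
- The SAE route is circular, because that definition opens "An adverse event (AE) or suspected adverse reaction is considered". A reader who has already ruled the value out as an AE must decide whether it can be a suspected adverse reaction, a term these sections do not define separately.

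**Liver enzymes.** The exception probably means grade 2 or higher, in which case they are covered. On the exact words, grade 3 and 4 elevations are not excepted. The point is therefore firmest for non-hepatic values.

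**Timing.** Baseline samples precede dosing, and section 8.3 schedules laboratory tests at baseline and 4 weeks. Day 28 is thus the only scheduled post-dose panel, and a silent abnormality would normally first appear there. By then dosing is ending for that subject, so a halt would chiefly protect others. The 7.2 safety visit adds no later look, because for a completer it is the visit at which the value was found.

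**Comparator for the fix.** Section 8.4.4 treats a condition "present at the time that the participant is screened will be considered as baseline and not reported as an AE". The mineral panel, hs-CRP and fasting lipids are not drawn at screening but first at Day 0, so a rule for new or worsened values needs the last pre-dose value as its reference.

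**The case against.** The strongest reply is that the gap matters little because escalation does not depend on AE status. Section 8.5 covers any occurrence that is unexpected, at least possibly related, and suggestive of greater risk than was known. Section 6.2.2 records no known toxicology, and the events listed as expected in 8.4.3.3 are vasovagal symptoms and bruising. A related grade 3–4 value could readily qualify and go to the IRB, one of the two bodies named in 7.1. This stands, and it is a main reason to rate the point low. It does not replace the halt: 8.5 is a reporting duty with its own test, its timelines sit in a policy outside these documents, and suspension under Study Discontinuation and Closure is discretionary.

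A second reply is that keeping isolated laboratory values out of AE counts, while reviewing them clinically, is a legitimate choice, and that the clauses can be reconciled by letting the specific rule govern. That is largely right. But reconciled in this way, they give exactly the result at issue: a severe related value outside the mandatory triggers.

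A third reply is that the setting is benign: 28 days of a supplement, 27 planned completers, and two published human studies with no associated adverse events (2.3.1). This supports a low rating too.

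A reader might infer that every safety visit is lost. The documents do not support that. Only the footnote B visit depends on an AE; the 7.2 visit does not.

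**Conclusion.** The point holds as a low-severity correction to safety wording. As written, 8.4.4 takes a related symptom-free grade 3–4 laboratory value out of the automatic halt, required attribution, required follow-up to resolution and the footnote B visit. This rests on a literal reading of the laboratory sentence as the specific rule. For liver enzymes it rests further on reading the exception as grade 2 only, which is probably not what was meant.

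The size cannot be put as a probability. The documents give no rate for such values, and the safety record they cite suggests that it is low. A reader might infer that the trial is likely to miss a stopping event, or that severe laboratory findings would go unexamined. Neither follows. Investigators may apply the other clauses, and evaluation, unanticipated-problem reporting, discretionary suspension and DSMB review all remain. The primary IL-17 comparison does not depend on AE classification.

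**What to change.** Amend the exception in 8.4.4 to read: *except for liver enzyme elevations of grade 2 or higher, and any other laboratory abnormality that is grade 3 or higher and new or worsened from the last pre-dose value, which will be recorded, graded and attributed as AEs*.

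The halt, attribution, follow-up and footnote B then apply through their existing wording. Symptom-free grade 2 non-hepatic values stay outside the AE category and are documented if clinically significant. They could not trigger 7.1 in any case, and the team can lower the threshold if it wants them followed as AEs.

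The cost is one sentence, a few more AE entries, and perhaps an occasional pause of the whole study for a laboratory-only event judged related. The study team is blinded (6.3), so that event could occur in a placebo subject. No scheduled test is added: the Day 28 panels are already planned and safety-visit testing stays optional.

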8.4.5 Adverse Event Reporting

Grading and attribution of AE's captured in the database will be determined by the Principal Investigator or Associate Investigator's designated on the designation log.

8.4.6 Serious Adverse Event Reporting

The study investigator will immediately report to the NHLBI Clinical Director any serious adverse event, whether or not considered study intervention related, including those listed in the protocol and must include an assessment of whether there is a reasonable possibility that the study intervention caused the event.

All serious adverse events (SAEs) will be followed until satisfactory resolution or until the site investigator deems the event to be chronic or the participant is stable.

Any SAE considered at least possibly related to the supplement will be reported to the DSMB within 14 days of the investigator being notified of the event.

8.4.7 Events of Special Interest

N/A

NIH Intramural IRB and NHLBI Clinical Director (CD) Reporting

Template version date 07-29-2019

Abbreviated Title: NR in psoriasis

Version Date: 07/21/2023

Expedited Reporting

Events requiring expedited reporting will be submitted to the IRB per HRPP Policy 801 “Reporting Research Events”.

Reports to the IRB at the time of Continuing Review (CR):

The PI or designee will refer to HRPP Policy 801 “Reporting Research Events” to determine IRB reporting requirements.

Reports to the CD:

The PI or designee will refer to NHLBI DIR guidelines to determine CD reporting requirements and timelines.

8.4.8 Reporting of Pregnancy

If pregnancy occurs during the course of this study a reportable event form will be submitted to the Clinical Director and the IRB.

Pregnancy itself is not regarded as an SAE unless there is suspicion that the investigational product under study may have interfered with the effectiveness of a contraceptive medication. Any SAEs associated with pregnancy (i.e. congenital abnormalities/birth defects/spontaneous miscarriages or any other serious events) must additionally be reported as such using the SAE report form. Monitoring of the pregnancy through chart review (per HIPPA guidelines) will continue until conclusion of the pregnancy, and then subject will be taken off study.

8.5 UNANTICIPATED PROBLEMS

8.5.1 Definition of Unanticipated Problems (UP)

Please refer to Policy 801 for current Definitions.

Any incident, experience, or outcome that meets **all** of the following criteria:

- Unexpected in terms of nature, severity, or frequency given (a) the research procedures that are described in the protocol-related documents, such as the Institutional Review Board (IRB)-approved research protocol and informed consent document; and (b) the characteristics of the participant population being studied; and
- Related or possibly related to participation in the research (“possibly related” means there is a reasonable possibility that the incident, experience, or outcome may have been caused by the procedures involved in the research); and
- Suggests that the research places participants or others (which many include research staff, family members or other individuals not directly participating in the research) at a greater risk of harm (including physical, psychological, economic, or social harm) than was previously known or expected.

8.5.2 Unanticipated Problem Reporting

The investigator will report unanticipated problems (UPs) to the NIH Institutional Review Board

Template version date 07-29-2019

Abbreviated Title: NR in psoriasis

Version Date: 07/21/2023

(IRB) as per Policy 801.

8.5.3 NIH Intramural IRB Reporting of IND Safety Reports

N/A

9 STATISTICAL CONSIDERATIONS

9.1 STATISTICAL HYPOTHESIS

Supplementation with NR will blunt systemic immune activation in mild/moderate psoriasis.

Primary Endpoint(s): The primary outcome will be the change in the T_H17 cell cytokine IL-17 secretion in response to T-cell differentiation comparing the baseline to NR response after 28 days.

Exploratory Endpoint(s):

- Evaluate the effect of NR on the T cell transcriptome
- Explore the effect of NR on low-density granulocytes and neutrophils

